4.4 Methods for additional analyses

Secondary outcomes involving proportions will be analyzed using methods for Binomial distributions akin to the ones described above. Continuous measurement will be summarized using means and standard deviation. The percent of people with a specific AE will be reported in prespecified groups. The percent of subjects with adverse events in subjects that have at least one therapeutic shave will be compared with the percent of subjects with adverse events that have no therapeutic shaves using Fisher's exact test.

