## 15.2 Sample size

Analyses during the Phase C study may lead to a change of algorithm (i.e., refinement of the threshold). The tumor detection algorithm will be locked in place before the start of the pivotal study based on the results of this Phase C study. The tumor detection algorithm lock will be contingent on the accrual of enough “pathology positives” to yield a ~7% margin of error in sensitivity. “Pathology positive” is defined as an imaged surface that contains cancer as identified by histopathology. A single patient may give more than one “pathology positive” image. Given that 19 pathology positive samples were acquired during the Phase B study, an additional 32 pathology positives will be needed to achieve the targeted margin of error. Because 40 patients in the Phase B study yielded 19 pathology positives, we expect to image approximately 67 patients during the training portion of the pivotal study (Phase C) before locking the threshold algorithm in place for the pivotal study. However, because the incidence of pathology positives is largely unknown at the sites participating in the future pivotal trial, the study will continue until enough patients have been enrolled to collect the data to lock the tumor detection algorithm. This number of patients will not exceed 250 patients.

Based on our experience from Phase A and Phase B of the feasibility study, we anticipate that with up to 5 patients per surgeon and approximately 1-3 surgeons per site, we may identify and address any site-specific and surgeon-specific issues related to the use of the LUM Imaging System. We anticipate expanding the study to a maximum of 20 sites; thus, we expect to have up to 250 patients in Phase C.

If tumor detection algorithm verification is complete, yet not all surgeons and clinical staff have completed training on the LUM Imaging System, these institutions can continue the training process as a lead-in to any Luminell Imaging Studies they may participate in the future.

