Although no pre-defined, hypothesis tested endpoints were included in the protocol, we will perform data analyses based on the proposed endpoint of the pivotal study protocol CL0007r07.

2 Analysis Populations

- Safety (SAF) population: the safety population includes all subjects who received study drug.
- Modified Intention To Treat (mITT) population: includes all SAF subjects excluding subjects who are not able to be imaged with the LUM Imaging System. That is, the mITT population includes all patients imaged with the LUM Imaging System and will be used as the primary analysis population for the efficacy metrics outlined in section 3.
- Per-Protocol Population: Includes mITT subjects who complete all study evaluations and are without any major protocol deviations. This per protocol population will be used to evaluate the efficacy metrics outlined in section 3.

3 Efficacy metrics analysis

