3.5 Safety measurements analysis

The safety measurements include the following:

- a. Adverse events stratified by severity and relatedness to drug/device
- b. Serious adverse events stratified by severity and relatedness to drug/device
- c. Adverse events by preferred term (sorted by descending occurrences for each preferred term)
- d. Summary of adverse events, overall and split by expectedness to drug/device
- e. Comparison of adverse events in subjects that have at least one therapeutic shave versus subjects that have no therapeutic shaves

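### The SAP's adverse-event comparison by therapeutic shave is a lone Fisher p-value; it should report a risk difference with a 95% interval and be labelled descriptive, unpowered and confounded.

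*SAP*

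**What the plan says.** SAP 3.5, item e, lists as a safety measurement a "Comparison of adverse events in subjects that have at least one therapeutic shave versus subjects that have no therapeutic shaves". SAP 4.4 supplies the method: the percent with adverse events in the shaved group "will be compared with the percent of subjects with adverse events that have no therapeutic shaves using Fisher's exact test". No effect measure, interval for the difference, significance level or power is given. The rest of SAP 3.5 and 4.5 consists of tabulations of adverse events.

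Other proportions are treated differently. SAP 4.2 (residual cancer removal) and SAP 4.3 (sensitivity, specificity, Youden Index) each call for a point estimate with a two-sided 95% interval. The Youden interval is built as a difference between two proportions, which is the kind of interval missing here.

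The size comes from Protocol 15.2, which aims at a margin of error of about 7% for sensitivity. It says "an additional 32 pathology positives will be needed to achieve the targeted margin of error" and gives an expected count of about 67 imaged patients. Enrolment may continue beyond that: "This number of patients will not exceed 250 patients". SAP section 1 adds the caveat "Although no pre-defined, hypothesis tested endpoints were included in the protocol". SAP section 2 defines the population for safety: "the safety population includes all subjects who received study drug".

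**The concern.** The LUM procedure removes extra tissue, up to two therapeutic shaves per orientation (Protocol 5.4.5 and 8.2). Whether that adds adverse events is a natural question, and SAP 3.5e is the only place in the SAP where adverse events are compared inferentially. A p-value above 0.05 from this test could come from data that exclude a worthwhile increase or from data that exclude almost nothing, and the p-value does not tell the two apart. At stake is how much a reader of the Phase C report can learn about added harm before the pivotal study.

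**Working it through.** **1. The plan's own size.** Protocol 15.2 gives 19 pathology positives in 40 Phase B patients and 32 more needed. Then 32 / (19/40) = 67.4, which reproduces the stated 67. With 19 + 32 = 51 positives, the 95% half-width is 1.96 × √(0.93 × 0.07 / 51) = 7.0 points. The 93% sensitivity is an assumption that makes the target fit; the documents do not state it. No safety quantity enters the calculation.

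**2. What the p-value hides.** Illustrative counts, with S = shave and N = no shave. The Newcombe interval for d = p_S − p_N uses the Wilson limits (l, u) of each proportion:

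- lower = d − √[(p_S − l_S)² + (u_N − p_N)²]
- upper = d + √[(u_S − p_S)² + (p_N − l_N)²]

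For 3/34 versus 3/33: p_S = 8.82% (Wilson 3.05 to 22.96) and p_N = 9.09% (3.14 to 23.57), so d = −0.27.
- Lower = −0.27 − √(5.78² + 14.48²) = −15.9.
- Upper = −0.27 + √(14.14² + 5.95²) = +15.1.

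For 13/125 versus 12/125: p_S = 10.40% (6.18 to 16.98) and p_N = 9.60% (5.58 to 16.03), so d = +0.80.
- Lower = 0.80 − √(4.22² + 6.43²) = −6.9.
- Upper = 0.80 + √(6.58² + 4.02²) = +8.5.

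| Counts (S vs N) | Fisher p | Difference, points | Newcombe 95% CI |
|---|---|---|---|
| 3/34 vs 3/33 | 1.0 | −0.3 | −15.9 to +15.1 |
| 6/34 vs 3/33 | 0.48 | +8.6 | −8.7 to +25.5 |
| 13/125 vs 12/125 | 1.0 | +0.8 | −6.9 to +8.5 |
| 20/200 vs 5/50 | 1.0 | 0.0 | −11.9 to +7.5 |

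The first and third rows have the same p-value, but the first interval is about twice as wide. The second row is close to an observed doubling and is far from significance. This step needs no assumption about power.

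**3. Power for a doubled rate.** Exact power of the two-sided Fisher test, by full enumeration of both binomial distributions. Assumptions: alpha 0.05 (SAP 4.4 gives none), adverse-event rate in the no-shave group as shown and doubled in the shave group, and 50%, 80% or 90% of patients shaved.

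| N (shave/no shave) | 5→10% | 10→20% | 20→40% | 30→60% |
|---|---|---|---|---|
| 67 (34/33) | 3% | 13% | 36% | 65% |
| 67 (54/13) | 0.4% | 3% | 21% | 42% |
| 67 (60/7) | 0.3% | 0.2% | 12% | 29% |
| 250 (125/125) | 24% | 54% | 92% | 99.7% |
| 250 (200/50) | 12% | 35% | 76% | 97% |
| 250 (225/25) | 0.4% | 14% | 46% | 79% |

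With 50% to 80% of patients shaved, power for a doubling reaches 50% at a base rate of about 25% to 33% for N = 67, and about 10% to 14% for N = 250. For 80% power on 10% versus 20%, about 199 patients per group are needed, or 219 with continuity correction.

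**4. Single rates.** Protocol section 11 reports one anaphylactic reaction among the first 4 Phase C patients, and Table 3 of Protocol 11.2 rates the event as probable and serious. If exactly one such event were seen, the Clopper-Pearson 95% upper limit would be 8.0% of 67 patients or 2.2% of 250. No interval is specified for this rate.

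**The case against.** **Power.** A reader might infer that the test usually misses a doubling of the adverse-event rate. The documents do not support that as a general statement, because they give neither the event rate nor the split. Protocol 12.1.1 counts events whether or not they are related to the study, the patients are undergoing surgery, and Table 3 lists urine discoloration as frequent, so a high base rate is possible. At 250 patients split evenly, power for 20% versus 40% is 92%. Nor is 67 a fixed size: Protocol 15.2 lets enrolment run to 250. A small no-shave group is possible but not established. The share of LUM-positive patients is not stated, and in the safety population patients who were injected but not imaged would count as having no shave.

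**Scope and intent.** A reader might infer that this is the only inferential safety analysis, or that a non-significant result will be presented as proof of safety. Neither follows. Protocol Appendix D plans an ANOVA on histamine, tryptase and complement with a 0.05 criterion. No passage equates non-significance with safety, and SAP section 1 disclaims hypothesis-tested endpoints. It would also be too strong to say that a non-significant result is uninformative: 13/125 versus 12/125 excludes a rise above 8.5 points.

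**Output.** The two percentages, the adverse-event tables and subject-level listings are planned, so a reader could compute an interval. The general sentence on binomial methods in SAP 4.4 might be read as giving an interval for each group, though not for the difference. Safety oversight also rests on stopping rules, a medical safety monitor and a DSMB.

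**What stands.** These points limit the claim about power and remove any claim about intent. They do not answer the reporting gap: the SAP specifies an interval for the Youden Index, itself a difference of proportions, and none for the difference in harm. Confounding cuts both ways. The study is non-randomized and the groups form after enrolment, from imaging findings and surgical decisions. An interval does not cure that, and a bare p-value does not disclose it.

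**Conclusion.** The point holds as a reporting weakness of moderate weight. The SAP's only inferential adverse-event comparison rests on a p-value alone, in a study sized for sensitivity, and that p-value cannot by itself show absence of added harm. The same p = 1.0 can accompany an upper limit of +15.1 or +8.5 points. Power for a doubling runs from under 1% to 99.7% over the assumed grid (N of 67 or 250, base rates of 5% to 30%, 50% to 90% shaved, two-sided 0.05), so low power is a range that depends on unknowns and not a fixed property of the plan. The need for an interval does not depend on those assumptions.

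**What to change.** In SAP 4.4, make the risk difference (shave minus no shave) with a two-sided 95% interval, for example Newcombe, the main reported result, and keep Fisher's test as supplementary. Add a statement that the comparison is descriptive and unpowered, that it is confounded because the groups are non-randomized and form after enrolment, and that absence of added harm will not be concluded from p > 0.05.

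Optionally, in SAP 4.5 add exact (Clopper-Pearson) 95% intervals for the rates of serious adverse events and of anaphylaxis/hypersensitivity in the SAF population, so that low or zero counts carry an upper bound.

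The cost is SAP wording and a few lines of code, with no new data and no change to study conduct. The downside is that the intervals may be wide and will show how little the study can exclude.

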4.5 Safety analysis

Safety data will be reported as:

- Adverse events stratified by severity and relatedness to drug/device.
- Serious adverse events stratified by severity and relatedness to drug/device.
- Adverse events coded per MedDRA guidelines
- Adverse events by preferred term per MedDRA (sorted by descending occurrences for each preferred term).

Adverse events will be reported by the clinical trial sites and data is recorded in the eCRF. However, a Luminell representative is responsible for assigning the 'expectedness' of any event as described in the study plans or protocols

4.5.1 Complement activation data

LUMICELL CONFIDENTIAL

This document is confidential. Do not disclose or use except as authorized.

Raw data will be generated by Lab Connect for blood samples collected in response to an adverse event or as part of the sub-study. These raw data sets are data external to the eCRF.

4.6 Protocol Deviations

Protocol Deviations are identified by either Luminicell personnel or clinical sites. Deviations are reported in the eCRF. Luminicell personnel will adjudicate these events as described in the study plans and procedures. The adjudication will include an impact to data capture and may be removed from the efficacy analysis. The Protocol Deviations external data set will be used for analysis and not generated by the protocol deviations reported in the eCRF.

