#### 5.4.2 Recording surgeon's decisions

[figure not shown]
During the LUM imaging procedure, if the surgeon decides to take a different action than the one suggested by the LUM Imaging System, the reason must be documented. The surgeon must notify the computer operator or clinical coordinator at that moment and they will note the reason in the study worksheets. This information will then be transferred to the case report forms. This is of utmost importance for evaluating the impact of the LUM Imaging System in guiding removal of tissue to obtain negative margins. If a shave is not taken when indicated by the Luminicell system, a protocol deviation will be recorded.

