4.7 Reported device issues

Device issues as reported or interpreted by the clinical site are captured in the eCRF. These reported device issues will be evaluated and adjudicated by Luminicell personnel for impact to subject safety, impact to data capture, and categorization. Issues that resulted in an impact to data capture may be removed from the efficacy analysis. The 'Device Issues' external data set will be used for analysis and not generated by the device issues reported in the eCRF.

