4.8.3 Missing and spurious data

During Luminicell-guided imaging, when there is not enough tissue to be removed (e.g. too close to skin or too close to the chest wall) no LUM image shall be recorded because it does not generate an actionable result.

In the case where the LUM Imaging System indicates that a therapeutic shave needs to be removed but the surgeon decides not to follow this guidance, the reason for not doing so will be recorded in the patient's CRF or during imaging. These instances are considered as a protocol deviation. There are other cases when the shavings reach protocol limits so no shaving will be performed. In these cases, the data will be included in the performance evaluation as is - that is no Luminicell-guided shave-taken will be considered as no removing of cancer or positive margin. However, they will be considered as a detection if there are cancer in the re-excision or if there are positive margins on the corresponding orientations.

Occasionally, a cavity image may be recorded from an unintended region or the image may be deemed as low quality (blurry, out of focus, etc.). For example, the surgeon realizes that he/she placed the device in the wrong location within the cavity after recording an image. Since the LUM software does not allow to overwrite saved images, this situation will be documented, the image will be labeled as "image retaken", "eval", "initialscan" or "transient" and the image will be excluded from the analysis. In addition, images labeled as "lens issue" will be considered as a device malfunction and will be excluded from the analysis.

Other cases are handled as follows:

- When a patient was prescribed Letrozole adjuvant therapy prior to surgery, the patient will be removed from the device performance evaluation.
- When the time from injection of LUM015 to lumpectomy incision is greater than 6 hours due to unplanned surgical delays, the patients will be removed from the device performance evaluation.
- For the re-excision rate endpoints, all patients undergoing a re-excision will be included in the analysis.
- When an image is indicated negative by LUM Imaging System but the shave is taken due to X-ray or pathology suggestion, it will be kept for sensitivity and specificity evaluation, however, for the analysis related to margins, it is conditional and described in g.

LUMICELL CONFIDENTIAL

This document is confidential. Do not disclose or use except as authorized.

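### SAP 4.6 and 4.7 allow discretionary removal from an unspecified efficacy analysis, which does not fit a primary population of all imaged patients and is not stated to be masked to pathology

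*SAP*

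**What the plan says.** SAP section 2 defines three populations. For efficacy it states that "the mITT population includes all patients imaged with the LUM Imaging System and will be used as the primary analysis population". Per-Protocol is the narrower set: "Includes mITT subjects who complete all study evaluations and are without any major protocol deviations". Both are to be used for the section 3 efficacy metrics, with mITT primary.

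SAP 4.6 covers protocol deviations. "Luminicell personnel will adjudicate these events as described in the study plans and procedures", and then: "The adjudication will include an impact to data capture and may be removed from the efficacy analysis". On the data source it adds: "The Protocol Deviations external data set will be used for analysis and not generated by the protocol deviations reported in the eCRF".

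SAP 4.7 applies the same approach to device issues, again adjudicated by sponsor personnel and analysed from an external data set: "Issues that resulted in an impact to data capture may be removed from the efficacy analysis".

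SAP 4.8.3 gives specific rules. Some data are kept: minor deviations (item f) and cases where no shave was taken although the system indicated one, of which it says "In these cases, the data will be included in the performance evaluation as is". Some are dropped: letrozole before surgery, more than 6 hours from injection to incision, shaves without a saved image (item e), and images carrying certain labels.

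Protocol 5.4.2 classes a declined shave as a deviation: "If a shave is not taken when indicated by the Luminicell system, a protocol deviation will be recorded". Protocol 5.4.6 and 8.1 take dye and extravasation patients out of the efficacy cohort. Protocol 15.3 includes imaged subjects in the imaging analysis unless otherwise specified, and 15.4 requires a rationale for other excluded subjects.

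**The concern.** A primary population of all imaged patients has value because membership is fixed by one objective event. Sections 4.6 and 4.7 add a second, discretionary gate. They do not say whether it acts on mITT or only on Per-Protocol, or whether it removes a patient, an orientation or an image. Two analysts working from this SAP could build different primary data sets.

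The study is non-randomized and open label (Protocol section 1). The sponsor also adjudicates discrepant margin status (SAP 4.8.3, item m), so pathology reaches the organisation that decides on removals. The SAP does not say whether the same people do both. Nothing in it prevents an adjudicator from knowing that a deviation or device issue falls on a missed cancer, a false positive or a patient in whom no residual cancer was found.

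At stake are the estimates of sensitivity, specificity, Youden Index and residual-cancer removal. SAP 3.2 and 3.3 label these as co-primary endpoints of the pivotal study, and Protocol 15.5 uses the combined Phase B and Phase C data to power that study. Optimistic estimates here would carry into its assumptions.

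**Working it through.** The plan states no figure for this point, so the main check is a comparison of texts. Arithmetic then shows how much weight a single removal carries.

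**Texts side by side**

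| Question | SAP section 2 | SAP 4.6 and 4.7 |
|---|---|---|
| Who is in the primary efficacy set? | Every imaged patient | Not stated; only the efficacy analysis in general |
| Where do deviations lead to exclusion? | Per-Protocol, if major | Anywhere in efficacy, if adjudicated as affecting data capture |
| Unit removed | Patient | Not stated |
| Masking or timing | Not stated | Not stated; procedures are in other documents |

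The two criteria also differ. Per-Protocol turns on a deviation being major, for which Protocol 12.9 gives only examples. Sections 4.6 and 4.7 turn on an effect on data capture.

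**Context from Protocol 15.2**

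- Patients expected: 32 × 40/19 = 67.4, which reproduces the protocol's approximately 67.
- Pathology positives at algorithm lock: 19 + 32 = 51.
- 95% half-width for sensitivity, 1.96 × √(p(1 − p)/51): 0.070 at p = 0.93, 0.082 at p = 0.90, 0.110 at p = 0.80. The stated margin of about 7% therefore corresponds to p of about 0.93. The protocol gives no assumed sensitivity.

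**Leverage of removals** (all counts of misses and of residual-cancer patients are assumed)

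- 32 Phase C positives, 3 misses: 29/32 = 90.6%. Remove one miss: 29/31 = 93.5%. Remove two: 29/30 = 96.7%.
- Same start, but the removal takes one true positive along with one miss: 28/30 = 93.3%. If it takes one true positive only: 28/31 = 90.3%.
- 51 positives, 8 misses: 43/51 = 84.3%. Remove four misses: 43/47 = 91.5%, a rise of 7.2 points.
- 51 positives, 4 misses: 47/51 = 92.2%. Remove all four: 47/47 = 100%, a rise of 7.8 points.
- Residual-cancer removal (SAP 3.2), 8 of 80 patients: 10.0%. Remove ten patients without residual cancer: 8/70 = 11.4%.

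On these assumptions, two to four removals that fall only on misses shift sensitivity by about 6 to 8 points, roughly the whole margin of error the protocol aims for. Removals that are not one-sided shift it much less, or downwards.

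The 32 and 51 count imaged surfaces, whereas SAP 3.3.2 measures sensitivity per tissue under a hierarchical truth standard. The examples show the order of size only.

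**The case against.** The strongest reply is that 4.6 and 4.7 are narrower than they look. Removal is tied to an effect on data capture, so a device issue in a patient with a missed cancer is removable only if capture was affected. Section 2 uses both mITT and Per-Protocol for the efficacy metrics, so the reference to the efficacy analysis may have been meant for Per-Protocol only. The procedures that 4.6 cites were not available here and may contain masking and timing rules. Protocol 15.4 requires a rationale for excluded subjects, SAP 3.4(m) reports device issues and their effect on data capture, site reports stay in the eCRF for comparison, and subject listings are planned. An external data set is a normal product of adjudication. No hypothesis is tested.

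Much of this stands. It limits the point but does not remove it. The wording is not confined to Per-Protocol, and mITT is the primary efficacy set. Judging whether capture was affected is itself discretionary. A rationale written after the result is known does not prevent a choice made with the result known, and 15.4 speaks of subjects, not of single images or orientations. Without a hypothesis test there is no type I error at issue, but estimates can still be biased.

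A reader might infer that the declined-shave rules collide outright, because such a shave is a deviation that 4.6 could remove while 4.8.3 keeps it. The documents do not support that strongly. The specific 4.8.3 rule most naturally governs, and declining a shave does not in itself impair image capture. What is missing is a statement of precedence.

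**Conclusion.** The point holds as an inconsistency between SAP section 2 and SAP 4.6 and 4.7, together with a missing safeguard. A discretionary rule of unstated scope sits over the stated primary population, and the SAP states neither masking to pathology nor completion before outcomes are merged. Following the plan as written could bias the accuracy and residual-cancer estimates that inform the pivotal study.

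A reader might go further and infer that the sponsor would remove data selectively, or that the estimates will be inflated. The documents do not support either inference. They leave outcome-aware removal open; they do not describe it. The sensitivity shifts of about 6 to 8 points are worst cases on assumed counts in which only misses are removed. The actual effect could be nil.

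The conclusion rests on the SAP text alone. If the unseen procedures already provide masking and timing, the SAP need only cite or restate them, but the population and unit would still need to be stated. For a feasibility study this is worth correcting and cheap to correct.

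**What to change.** 1. State in 4.6 and 4.7 that discretionary removals apply only to Per-Protocol or sensitivity analyses, and name the unit removed. Let the primary mITT analysis omit only data that meet exclusions already pre-specified: dye (Protocol 5.4.6), extravasation (Protocol 8.1), and the SAP 4.8.3 rules and image labels. Reword the mITT definition to name these. Keeping literally every imaged patient would override them.
2. State that the specific rules in 4.8.3, including keeping declined-shave data, take precedence over 4.6.
3. Have the existing adjudicators work from listings without pathology, and without the LUM result where the issue does not itself reveal it. A declined shave does reveal it, so masking to pathology is the essential part. Complete adjudication before pathology is merged.
4. List each removal with its reason and the cell of the 2x2 table it would have occupied, and report results with and without removals.

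The cost is SAP wording and a small amount of extra listing work; no new patients or visits are needed, and the work can stay with the existing adjudicators. The downside is that primary accuracy may be slightly less favourable, because cases with capture problems outside the pre-specified exclusions stay in.
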